5.4. Data Collection

Table 1 depicts the assessments, measurements, and time points for the data collection. We will administer patient-reported measures for 48 weeks from enrollment. We selected a longer administration period in the current study as the median survival for patients with lung cancer is now approximately one year. The study assessment battery takes approximately 20 minutes to complete.

Table 1. Summary of data collection instruments and time-points.

Self-Report Measure	Baseline	Every 6 weeks*	Week 12	Week 24	Week 36	Week 48
Demographic Questionnaire	X					
Self-Administered Comorbidity Questionnaire (SCQ)	X					
Functional Assessment of Cancer Therapy-Lung (FACT-L)*	X	X*	X	X	X	X
Patient Health Questionnaire-9 (PHQ-9)	X		X	X	X	X
Prognosis and Treatment Perceptions Questionnaire (PTPQ)	X		X	X	X	X
Brief Cope	X		X	X	X	X
EuroQol – 5 Dimension (EQ-5D)	X		X	X	X	X
Support Service Utilization Item					X	

*Step 1 patients will complete the FACT-L every 6 weeks for a minimum of 12 months and up to 18 months from enrollment

5.4.1. Data from Electronic Health Record:

Clinical information regarding tumor type (NSCLC, small cell lung cancer, and mesothelioma), current treatment regimen, date of diagnosis of incurable disease,

previous diagnosis of early stage disease, tumor genotype, and ECOG Performance Status will be collected at baseline.

Health care utilization data will be collected after death or at 12-months from the date the last patient enrolled on the study. We will collect data on: (1) outpatient and inpatient PC visits; (2) chemotherapy and radiation therapy administration; and (3) emergency department, hospital and intensive care unit admissions. EOL care measures will include referrals to and length of stay on hospice and location of death.

5.4.2. PC Cost and Resource Utilization Data:

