7.3. Exploratory Endpoints

- 7.3.1. To compare the longitudinal patterns in QOL in patients assigned to stepped PC versus early integrated PC, as measured by repeated assessments of FACT-L.
- 7.3.2. To compare the superiority of stepped PC versus early integrated PC with respect to cost-effectiveness.
- 7.3.3. To compare coping strategies in patients assigned to stepped PC versus early integrated PC.
- 7.3.4. To compare prognostic understanding in patients assigned to stepped PC versus early integrated PC.
- 7.3.5. To compare depression in patients assigned to stepped PC versus early integrated PC.
- 7.3.6. To compare health care utilization at the end of life (i.e., emergency department visits, hospitalizations, and chemotherapy administration) in patients assigned to stepped PC versus early integrated PC.

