7.4. Sample Size and Power Calculation

The primary endpoint of the study is to establish that stepped PC is non-inferior to early integrated PC in the change in QOL, as measured by the FACT-L at week-24. Although the primary endpoints in our previous studies assessed the change in FACT-L from baseline to week-12, we chose to focus on QOL at 24 weeks as the life-expectancy of patients with advanced lung cancer has improved over the last few years. Thus, examining QOL at 12 weeks may overlook important differences between groups as the disease progresses. In our most recent trial of early integrated PC versus standard oncology care, we observed a 7.5-point difference in the FACT-L at week-24 favoring the integrated PC group. Thus, we chose a conservative non-inferiority margin of 4.5 points, which is slightly less than 50% of the previously observed advantage with early integrated PC compared to oncology care alone. As a 6-point difference in FACT-L score is considered the lowest range of a clinically meaningful difference, our non-inferiority margin would not reach the threshold of clinically meaningful difference in QOL.⁵⁵ With

188 patients per group, we will have >80% power to establish the non-inferiority of stepped PC compared to early integrated PC on the FACT-L with a one-sided alpha of 0.05, and a non-inferiority margin of 4.5 points. We are currently observing 35% missing data across sites at 24 weeks, primarily due to progressive illness or death. Therefore, we increased our sample size to 255 per group to ensure we have adequate power to assess for non-inferiority of stepped PC.

Our study also has adequate power to assess for non-inferiority of stepped PC compared to early integrated PC in EOL communication and hospice length-of-stay. With a sample size of 510, we will have >80% power, with a one-sided alpha of 0.05, to reject the hypothesis that patient-reported EOL communication with stepped PC would be 10% lower than early integrated PC, assuming that the rate of EOL communication in the early integrated PC group is 30% (based on our recent trial). With this sample size, we will also have >80% power to establish the non-inferiority of stepped PC compared to early integrated PC in hospice length-of-stay with a one-sided alpha of 0.05, and a non-inferiority margin of 7 days. We were conservative with our power estimations by using the highest observed standard deviation for all outcomes from prior studies.

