**Table 1. Study Questionnaires**

Self-report measure	Baseline	Every 6 weeks	Weeks 12, 24, 36 & 48	Scoring
Demographics	X			n/a
SCQ	X			Range: 0-45 (higher is worse medical condition)
FACT-L	X	X 	X	Range: 0-136 (higher is better QOL)
PHQ-9	X		X	Range: 0-27 (higher is worse depression)
PTPQ	X		X	n/a

Brief Cope	X		X	Range: 2-8 for each facet (higher is more engagement in coping style)
EQ-5D	X		X	VAS Range: 0-100 (higher is better health state)
Support Service Utilization Item			X 	

 Step 1 patients completed FACT-L every 6 weeks for up to 18 months from enrollment.

 Collected only at week 24.

EQ-5D, EuroQol—5 Dimension; FACT-L, Functional Assessment of Cancer Therapy-Lung; PHQ-9, Patient Health Questionnaire-9; PTPQ, Prognosis and Treatment Perceptions Questionnaire; SCQ, Self-administered Comorbidity Questionnaire.

The primary outcome is patient-reported quality of life at 24 weeks from enrollment, as measured by the FACT-L.

The secondary outcomes are:

1. Patient report of patient-clinician communication about EOL care preference using the following item on the PTPQ: “Have you and your doctors discussed any particular wishes you have about the care you would want to receive if you were dying?” analyzed as “yes” versus “no.” The patient’s final assessment will be used.
2. Length of stay on hospice (in days) among patients who die during the study, as documented in the EHR.
3. PC resource utilization; specifically, the number of outpatient PC visits per patient during the study, as documented in the EHR.

The exploratory outcomes are:

1. Rate of change in quality of life from baseline to week 48, as measured by the FACT-L.
2. Cost-effectiveness as assessed by costs relative to quality adjusted life years. **Note:** Plans for the analysis of cost-effectiveness are not described in this SAP.
3. Patient-reported coping strategies at week 24, as measured by eight subscales of the Brief Cope, including subscales measuring emotional support, positive reframing, active coping, acceptance, self-blame, denial, spiritual coping, and behavioral disengagement, as well as higher-order factors reflecting active coping and avoidant coping).
4. Patient-reported prognostic understanding at week 24, based on relevant items on the PTPQ, including:
  - a. Patient’s primary goal of current cancer care. Responses will be dichotomized based on whether the patient selected “to cure my cancer” versus any of the other options.

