## 7. Sample Size

Sample size calculations were performed to detect a non-inferiority margin of 4.5 points on the FACT-L at week 24, assuming a standard deviation of 17.5 points and a between-group difference of 0 points. 188 patients per group were required to achieve 80% power with a one-sided significance level of 0.05. To account for an anticipated 36% rate of missing data at week 24 due to loss-to-follow-up, withdrawal, or death, enrollment of 255 per group (510 total) was planned.

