#### *Exploratory Outcomes*

The rate of change in quality of life from baseline to week 48 (assessed by the FACT-L) will be compared between groups using a linear mixed effects regression model. This model will utilize FACT-L scores at each timepoint, with estimation via maximum likelihood. The model will include fixed effects for group assignment (stepped PC vs early integrated PC), time from baseline (in weeks), time-by-group interaction, and randomization stratification factors, as well as random intercepts for each patient.

Model-based estimates of the slope with 95% CI in each group and the difference in slopes between groups and its 95% CI will be reported.

The difference in means between intervention groups in patient-reported depression symptoms (assessed by PHQ-9) and coping strategies (assessed by subscales and higher-order factors of Brief Cope) at week 24, will be estimated for each outcome using a linear regression model with group assignment (stepped PC vs early integrated PC) and baseline score, as well as randomization stratification factors, as main effects. Model-based estimates of the mean with 95% CI in each group and the difference in means between groups and its 95% CI will be reported.

Rates of prognostic understanding at week 24, based on PTPQ items eliciting the patient's goal of cancer care ("to cure my cancer" vs any other option) and the patient's assessment of curability ("yes" vs "no") will be compared using generalized linear models specified with an identity link function and binomial response probability distribution. Model-based estimates of the rate with 95% CI in each group and the difference in rates between groups and its 95% CI will be reported.

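### Exploratory outcome 1 summarises FACT-L to week 48 as one linear slope per arm, which cannot show a temporary early loss, and no committed analysis estimates the arm difference at weeks 12, 36 or 48

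*SAP*

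**What the plan says.** Protocol 7.3.1 states the exploratory endpoint as: "To compare the longitudinal patterns in QOL in patients assigned to stepped PC versus early integrated PC, as measured by repeated assessments of FACT-L". Protocol 7.5 adds linear mixed models of the longitudinal data to examine change in QOL over several time points.

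SAP section 6 lists the corresponding outcome as "Rate of change in quality of life from baseline to week 48, as measured by the FACT-L". The model in SAP section 9 (Exploratory Outcomes) has group, time in weeks, their interaction, the stratification factors and a random intercept. Its reported output is "Model-based estimates of the slope with 95% CI in each group and the difference in slopes between groups", with the CI for that difference. It has no categorical visit, no curvature term and no contrast at a given visit. The SAP addendum does not touch this outcome.

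The other committed FACT-L analyses in SAP section 9, the primary regression and the sensitivity mixed model, both estimate the arm difference at week 24 only. Partially conditional models, which would give a mean at each time point, appear under Missing Data (SAP section 8) among sensitivity analyses that may be done.

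**The concern.** A linear slope is one number per arm, so it is informative when the arms diverge steadily. It is a poor summary when one arm falls behind and then catches up. That second shape is plausible here. Under Protocol 5.3.1, a step 1 patient moves to four-weekly visits only after FACT-L has fallen at least 10 points from baseline, so some loss comes before the more intensive care.

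The visits without a planned comparison are not incidental. Protocol 7.4 says of week 12 that "the primary endpoints in our previous studies assessed the change in FACT-L from baseline to week-12". On follow-up to week 48, Protocol 5.4 says: "We selected a longer administration period in the current study as the median survival for patients with lung cancer is now approximately one year". The data are collected at all four visits, but as written the report could describe the course of QOL without saying how far apart the arms were at three of them. In a non-inferiority trial, a summary that masks a temporary loss on the new strategy errs toward the study hypothesis.

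**Working it through.** **Inputs from the documents.** Visits at weeks 0, 12, 24, 36 and 48 (SAP section 6); SD 17.5 and 255 per group (SAP section 7); 6 points as the lowest clinically meaningful FACT-L difference (Protocol 7.4); 36% missing at week 24 (SAP section 7; Protocol 7.4 says 35%).

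**Assumptions.** The documents give no within-patient correlation and no retention at weeks 12, 36 or 48. I take correlation 0.5 to 0.7 and monotone dropout unrelated to outcome, with proportions observed of 1/0.80/0.64/0.55/0.45 or 1/0.85/0.64/0.50/0.40.

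**Plan's own figure.** The SAP states that "188 patients per group were required to achieve 80% power with a one-sided significance level of 0.05", for a margin of 4.5 points, SD 17.5 and a true difference of 0. Check: 2 × 17.5² × (1.645 + 0.842)² / 4.5² ≈ 187.0, rounded up to 188, with power 80.2%. The figure reproduces. No precision is stated for the slope outcome.

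**Complete data.** Let d(t) be the stepped-minus-integrated difference at week t. With balanced data the random-intercept model gives

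slope difference = Σ(t − 24)·d(t) / Σ(t − 24)², where Σ(t − 24)² = 576 + 144 + 0 + 144 + 576 = 1440.

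For a 6-point loss at week 12 only: (−12)(−6)/1440 = +0.05 per week, and × 48 = **+2.4 points, favouring stepped care**. The mean difference over the five visits is −6/5 = −1.2. The fitted line therefore has an arm difference of −1.2 − 24 × 0.05 = −2.4 at baseline, where the true difference is 0, and −1.2 + 24 × 0.05 = 0 at week 48.

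**With dropout.** The table gives the expected slope difference per 48 weeks under the same model (negative means stepped care is worse). The SE under dropout is 1.45 to 1.91 in every row.

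| True loss on stepped care | Complete data | Assumed dropout |
|---|---|---|
| 6 at week 12 only | +2.4 | +1.65 to +1.83 |
| 6, 4, 2, 0 at weeks 12, 24, 36, 48 | +1.6 | +0.05 to +0.44 |
| 6 at week 36 only | −2.4 | about −2.7 |
| 6 at week 48 only | −4.8 | −3.9 to −4.0 |
| 6 at weeks 36 and 48 | −7.2 | −6.6 to −6.8 |
| 6 at every visit from week 12 | −4.8 | −5.7 to −6.0 |

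For the first row, the expected 95% interval under dropout runs from 1.83 ± 1.96 × 1.45 = (−1.0, 4.7) to 1.65 ± 1.96 × 1.91 = (−2.1, 5.4). Both include 0. In 40 simulated trials with retention 1/0.80/0.64/0.512/0.41, the estimate was positive in 90% and the interval lay wholly above 0 in 30%.

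**Wider assumptions.** With 20% to 52% left at week 48 and correlation 0.3 to 0.7, the week-12-only loss still gives +1.3 to +1.8. The gradually recovering loss then ranges from about −1.4 to +0.7, so under heavy dropout it can turn negative.

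**What a visit-specific estimate would show.** For a loss at week 12 only it shows −6 at week 12 and 0 at the later visits. The baseline-adjusted 95% half-width is 1.96 × 17.5 × √(1 − ρ²) × √(2/n). At week 12, n = 255 × 0.80 = 204 gives 2.9 (ρ = 0.5) or 2.4 (ρ = 0.7). Over weeks 36 to 48 it is about 3 to 4 points.

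**The case against.** The case on the other side is substantial, and much of it stands.

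- **The slope catches what the longer follow-up is for.** Late and sustained losses give a slope difference against stepped care. A reader might infer that a loss at any of weeks 12, 36 or 48 would be hidden or reversed. The table does not support that: reversal is confined to an early loss that recovers.
- **The outcome has no confirmatory role.** SAP section 8 gives exploratory outcomes no multiplicity adjustment and stresses estimates and intervals. A reader might infer that a week-12 loss would be reported as a benefit of stepped care. Only the point estimate leans that way, and under realistic dropout its interval would usually include 0.
- **A dip with recovery is conjecture at arm level.** The step-up rule acts on individuals at any follow-up time, Protocol 5.3.1 expects well under 40% to step up by week 24, and control patients can decline too. No passage predicts an arm-level loss that is present at week 12 and gone later. The shape is plausible, not expected.
- **Week 12 was set aside on purpose.** Protocol 7.4 chose week 24 because week 12 might miss differences that emerge as disease progresses. That settles the primary time point. It is no reason to leave the week-12 difference unestimated.
- **Other analyses give partial cover.** The sensitivity mixed model on weeks 0, 12 and 24 counts a week-12-only loss against stepped care: −6/3 = −2.0 at week 24 with complete data, about −2.3 to −2.4 with dropout. The optional partially conditional models could give visit means, so it would be wrong to say that the arms can never be compared at those visits. The gap is one of commitment.
- **The SAP does not contradict the protocol.** The protocol does not define longitudinal patterns as visit contrasts, and a slope comparison is one legitimate reading. It is, however, the narrowest one.

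**Conclusion.** The concern holds as a cheap improvement to an exploratory outcome. The SAP reduces a comparison of patterns to one slope difference, and no committed analysis estimates the FACT-L arm difference at weeks 12, 36 or 48.

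A 6-point loss on stepped care confined to week 12 would appear as +2.4 points per 48 weeks in its favour with complete data, or about +1.7 to +1.8 (SE 1.5 to 1.9) with dropout. A gradually recovering loss would appear as roughly no difference. Late or sustained losses keep the correct sign but lose their timing and size.

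The direction for a week-12-only loss is algebra with complete data and held under every dropout curve tried. The sizes rest on SD 17.5, 255 per arm, the assumed correlation and the assumed retention. The week-24 primary analysis and its non-inferiority conclusion are not affected.

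**What to change.** Keep the slope as a descriptive summary. Add, by a dated SAP addendum item, one repeated-measures model of FACT-L at weeks 12, 24, 36 and 48, with:

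- visit as a categorical factor and visit-by-group terms;
- baseline FACT-L and the stratification factors as covariates;
- an unstructured within-patient covariance;
- only the visits shared by both arms, leaving out the extra six-weekly scores collected from step 1 patients alone. The SAP's slope model uses scores at each time point and does not say whether those extra scores enter, so this should be stated for the slope too.

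Report the arm difference with its 95% CI at each of the four visits.

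The cost is a few lines of SAP text and one further model on data already collected, with no change to the sample size. The downside is a few more parameters and wider intervals at weeks 36 and 48 (half-width about 3 to 4 points on the assumptions above).

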7.5. Analysis Plan

The primary endpoint of the study is to establish that stepped PC is non-inferior to early integrated PC in QOL, as measured by the FACT-L at week-24. We will begin with descriptive and graphical summaries of the endpoints to evaluate whether the normality assumption is reasonable or if transformation is necessary. Based upon our prior study demonstrating statistical and clinically meaningful between group differences in the FACT-L at 24-weeks, the primary endpoint to compare patient FACT-L scores at week-24 between the study groups using a linear regression model controlling for randomization stratification factors, baseline values, and demographic and clinical factors (as necessary for any imbalances in baseline variables). We will also use linear mixed models of the longitudinal data, allowing us to account for dependency among means over time and to control for demographic and clinical factors when examining change between groups in QOL across multiple time points. We will also compare the number of PC visits between the two groups to ensure that the stepped PC model led to a reduction in PC visits.

We will compare depression (PHQ-9) and coping strategies (Brief Cope, including higher-order factors of the Brief Cope in our sample⁵²: active coping & avoidant coping) at week-24 between groups using linear regression models controlling for randomization

stratification factors, baseline values and selected demographic and clinical factors. We will then evaluate linear mixed models of the longitudinal data, as described above, to examine changes in these outcomes between groups across multiple time points.

To compare illness understanding as measured by the PTPQ between the two groups at week-24, we will analyze appropriate items using the appropriate model for the outcome of interest (e.g., linear regression or generalized linear models with an identity link function and binary response probability distribution) with adjustment for randomization stratification factors and any demographic and clinical factors that are imbalanced to assess differences between groups.

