## 6. Outcome Measures

Outcome data included self-report questionnaires collected prior to randomization (baseline) and then again at weeks 12, 24, 36 and 48 (with a  $\pm 2$ -week window) (see Table 1), as well as information collected from the EHR.

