  - b. Patient’s endorsement of the statement “My cancer is curable,” analyzed as “yes” versus “no.”
5. Patient-reported depression symptoms at week 24, as assessed by the PHQ-9.
6. Healthcare utilization at the end of life (i.e., the 30 days prior to death) among patients who die during the study, including:
  - a. Number of emergency department visits
  - b. Number of hospitalizations
  - c. Chemotherapy administration

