### *Missing Data*

Primary analyses will include available data without imputation of missing data. The characteristics of patients who complete versus do not the week 24 survey will be compared descriptively. Sensitivity analyses will explore how different assumptions about the missing data mechanisms affect estimated outcomes. These sensitivity analyses may include multiple imputation, terminal decline joint modeling, or partially conditional models, which provide estimates of the mean conditional on being alive and observed at each timepoint.

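### The SAP analyses depression and coping only at week 24 and omits, without explanation, the longitudinal models that the protocol plans for them

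*SAP*

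**What the plan says.** **Protocol.** Section 7.5 first compares PHQ-9 and Brief Cope at week 24 by linear regression. It then adds "linear mixed models of the longitudinal data, as described above, to examine changes in these outcomes between groups across multiple time points". Section 7.4 reports 35% missing data at 24 weeks and attributes it mainly to progressive illness or death.

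**SAP, outcomes.** Section 6 says questionnaires are "collected prior to randomization (baseline) and then again at weeks 12, 24, 36 and 48", and its Table 1 lists PHQ-9 and Brief Cope at each of these visits. The exploratory outcomes are narrower: "Patient-reported coping strategies at week 24, as measured by eight subscales of the Brief Cope" (outcome 3) and "Patient-reported depression symptoms at week 24, as assessed by the PHQ-9" (outcome 5).

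**SAP, analysis.** Section 9 says the week-24 difference "will be estimated for each outcome using a linear regression model with group assignment", baseline score and stratification factors. Among the exploratory outcomes, only the FACT-L trajectory "will be compared between groups using a linear mixed effects regression model".

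**SAP, missing data.** Section 8 states: "Primary analyses will include available data without imputation of missing data". It adds that sensitivity analyses will explore other missing-data assumptions, and lists methods that these may include. It names no scale. Section 7 anticipates 36% missing at week 24.

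**Addendum.** Item 2 substitutes the week-12 response when week 24 is missing, for prognostic understanding only. No item mentions the PHQ-9 or Brief Cope mixed models.

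**The concern.** Three of the four follow-up assessments of depression and coping (weeks 12, 36 and 48) have no specified analysis, although the protocol plans one and the data are collected in both arms. A patient who answered at week 12 and not at week 24 contributes nothing post-baseline to the planned comparison. Including all randomised patients by intention to treat does not bring that patient back, because the regression uses available week-24 scores.

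Protocol 5.2 says that earlier trials of palliative care improved PHQ-9. Readers will therefore ask whether fewer scheduled visits lose that benefit. If the link between mood and dropout differs between the arms, a week-24 regression on those who answered gives a distorted answer, and the SAP specifies no longitudinal result to set beside it.

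**Working it through.** The documents give no sample size, power or missing-data rate specific to PHQ-9 or Brief Cope, so no stated figure is in dispute. The check compares the texts, counts the patients affected, and then sizes the possible bias under labelled assumptions.

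**1. The texts side by side**

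| Outcome | Protocol 7.5 | SAP section 9 and addendum |
|---|---|---|
| FACT-L | week-24 regression and mixed models | week-24 regression, mixed model for week 24, mixed model to week 48 |
| PHQ-9, Brief Cope | week-24 regression, then mixed models | week-24 regression only |
| Prognostic understanding | week-24 models | week-24 binomial model; week 12 used if week 24 is missing |

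Only the middle row loses an analysis that the protocol plans, with no replacement.

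**2. Patients without a week-24 score.** This assumes that the overall missing rate applies to these scales.
- 510 × 0.35 = 178.5 and 510 × 0.36 = 183.6, so about 179-184 are missing.
- 510 × 0.65 = 331.5 and 510 × 0.64 = 326.4, so about 326-332 enter each regression. That is 255 × 0.64 = 163 to 255 × 0.65 = 166 per arm.

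**3. How many of these have a week-12 score.** The documents do not say. If the share is 25%, 50% or 75%, the number is about 45-46, 89-92 or 134-138. If instead 20% are missing at week 12 and nobody returns after dropping out, it is 510 × (0.80 − 0.64) = 82.

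**4. Possible bias, by simulation.** All inputs are assumptions:
- SD 5 and correlations of 0.5-0.7 between visits;
- a true stepped-PC disadvantage of 1.0 point at weeks 12 and 24;
- 18-20% missing at week 12 and about 35-39% at week 24;
- dropout after week 12 logistic in the score, with slopes in log-odds per SD.

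The comparison estimator regresses week 24 on week 12 and baseline, and week 12 on baseline. It is valid under missing at random. The table pools several runs.

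| Dropout after week 12 | Week-24 regression (truth 1.0) | Estimator using week 12 |
|---|---|---|
| On week-12 score, same slope in both arms (0 to 1.5) | 0.92-1.01 | 0.98-1.01 |
| On week-12 score, steeper by 0.5 in stepped PC | 0.75-0.82 | 0.99-1.02 |
| On week-12 score, steeper by 1.0 in stepped PC (0 vs 1.0) | 0.66 | 1.02 |
| On week-12 score, steeper by 0.5 in early integrated PC | about 1.10-1.15 | about 0.99-1.02 |
| On the week-24 score itself, 1.0 plus 0.5 in stepped PC | about 0.5-0.6 | about 0.6-0.7 |

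The fourth row was run with the arms' slopes swapped (1.0 against 0.5, and 1.5 against 1.0). The error changes sign and is somewhat smaller.

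**5. Bias against random error.** The SE of the week-24 difference is about 5 × √(1 − r²) × √(2/163), where r is the baseline correlation.
- r = 0.55 gives 0.46 and r = 0.70 gives 0.40.
- With equal slopes of 0.5 or more, one set of runs gave 0.92-0.99, a bias of 0.01-0.08. This is at most 0.08/0.40 = one fifth of an SE.
- With slopes differing by 0.5, a bias of 0.20-0.25 is 0.20/0.46 = 0.43 to 0.25/0.40 = 0.63 of an SE.
- Using week 12 made the SE only about 2% smaller. The case for the model rests on robustness more than precision.

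**The case against.** **The outcomes are exploratory.** They carry no multiplicity control, and the SAP reports them as estimates with intervals. Protocol 7.3 asks for longitudinal patterns only for quality of life; for coping and depression it says only that the arms will be compared. This stands and limits the importance. It does not explain why an analysis described in Protocol 7.5 is missing.

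**The SAP already provides for sensitivity analyses.** Section 8 commits to exploring missing-data assumptions and is not restricted to FACT-L. But the methods are optional and neither scale is named, so the gap is narrowed and not closed.

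**The bias is assumed.** A reader might infer that the plan understates harm to mood on stepped PC. The documents do not support that. They give no dropout by arm, and the direction cannot be predicted: step 1 patients have fewer scheduled visits but also complete FACT-L every six weeks. Nor do they show that patients with a week-12 but no week-24 score are mostly those who worsened. Protocol 7.4 gives progressive illness or death as the main reason for missing data overall, with no figure for this subgroup.

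**The simulation favours the model.** Where dropout depends only on an observed score, a missing-at-random method recovers the truth by construction. Protocol 7.5.5 itself treats missingness from progressive illness as a sign that data are not missing at random. In that case the model recovers only about 0.1 of the shortfall. After death there is no score to recover. This stands, and it is why the fix must state the assumption and the treatment of deaths.

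**Conclusion.** The discrepancy is real. The protocol plans longitudinal models for PHQ-9 and Brief Cope; the SAP keeps only a week-24 regression on available data and does not say why. About 179-184 of 510 patients are expected to have no week-24 score. Those among them with a week-12 score drop out of these comparisons, in a number that the documents do not give.

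The consequence is moderate and conditional. With equal score-dependent dropout in both arms, the week-24 estimate is close to unbiased. If the dependence differs by 0.5 log-odds per SD, the error is roughly a fifth to a quarter of a 1-point difference when it is steeper in stepped PC. It is somewhat smaller, and in the opposite direction, when it is steeper in early integrated PC. These sizes rest on the assumed SD, correlations, effect and dropout.

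It would be wrong to read the SAP as measuring these outcomes only at week 24: collection continues at weeks 12, 24, 36 and 48, and only the analysis is restricted. The primary and secondary conclusions are not affected.

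**What to change.** Add a dated item to the SAP addendum for PHQ-9 and the Brief Cope scores:

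- Fit a likelihood-based repeated-measures model with visits 12, 24, 36 and 48 as categories, visit-by-group terms, baseline score and stratification factors. State the covariance structure; the check above left it unrestricted. The protocol does not fix these details, so they are a specification choice.
- Report the week-24 arm difference with its 95% CI beside the existing week-24 regression, which stays.
- State that the model assumes missing at random, and how deaths are treated. One option is a partly conditional estimate among those alive, a method that SAP section 8 already lists.
- Record whether the item was written before the PHQ-9 and Brief Cope results were seen.

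If the sponsor prefers not to fit these models, the addendum should give the reason for departing from Protocol 7.5.

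**Cost.** The data are already collected, so this needs SAP wording and standard code. There are 11 outcomes: PHQ-9, eight subscales and two higher-order coping factors. That adds 11 unadjusted week-24 estimates, or 11 × 4 = 44 if every visit is reported, so the week-24 contrast should lead. The correction is only partial if missingness depends on unobserved scores.
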